3. SAMPLE SIZE DETERMINATION

Approximately 32 participants will be screened to achieve 21 participants randomly enrolled to either GSK2982772 or placebo in a 2:1 allocation ratio. Replacement participants may be randomised (up to approximately 6) into the study at the discretion of the Sponsor, to ensure that approximately 21 have completed the Week 4 visit.

The primary efficacy endpoint is PASI75 response (achieving $\geq 75\%$ improvement from Baseline in PASI score) at Week 12.

With a sample size of 21 participants there is approximately 99% probability of achieving a posterior probability of at least 97.5 that the true treatment difference over placebo is greater than zero. This is based on an assumed placebo response of 7%, an assumed true treatment difference of 55% and incorporating informative historical placebo data into the analysis. For the placebo arm an informative Beta (3.5, 46.5) distribution is assumed, with an effective sample size of 50 participants. For the active arm a vague Beta (1/3, 1/3) prior is used.

No sample size re-estimation is planned for this study.

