4. ANALYSIS SETS

Analysis Set	Definition / Criteria	Analyses Evaluated
Screened	
 • All participants who were screened for eligibility 	
 • Study Population
Enrolled	
 • All participants who signed the ICF, passed screening and were eligible for randomisation (regardless of whether the participant went on to be randomised). • Note screening failures (who never passed screening even if rescreened) and participants screened but never enrolled into the study (Reserve, Not Used) are excluded from the Enrolled analysis set as they did not enter the study. 	
 • Study Population
Randomised	
 • All participants who were randomly assigned to study intervention in the study. • Participant must have signed ICF and passed Screening. 	
 • Study Population

Analysis Set	Definition / Criteria	Analyses Evaluated
	
 • Data will be reported according to the randomised study intervention. 	
Intent to Treat (ITT)	
 • All participants who were randomised to study intervention in the study and who received at least one dose of study intervention. • Data will be reported according to the randomised study intervention. 	
 • Efficacy
Modified Intent to Treat (ITT)	
 • All participants in the ITT population who completed at least the Week 4 assessment. • Data will be reported according to the randomised study intervention. 	
 • Efficacy
Safety	
 • All participants in the enrolled population who received at least one dose of study intervention. • Data will be reported according to the actual study intervention received. 	
 • Safety • PD
COVID-19	
 • All participants in the Safety set who had a confirmed, probable or suspected COVID-19 case diagnosis. 	
 • COVID outputs

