5.2.2. Main analytical approach

The primary analysis will be produced for the ITT population.

The summary measure of interest is the difference in PASI75 response rates at Week 12 (Day 85) between GSK2982772 and placebo. Missing values will be imputed as non-responders.

The primary endpoint will be analysed using a Bayesian logistic regression model, details given in [Table 2](#). Summary statistics will be provided for the posterior distribution of the true difference in PASI75 response rate (GSK2982772 vs placebo) as well as posterior probabilities for a range of thresholds.

A non-informative prior will be used for the PASI75 response rate on GSK2982772 and covariates.

An informative prior will be used for the placebo response rate of the form: 90% weight on $Be(5.39, 69)$ and 10% on $Be(1/3, 1/3)$. The prior was derived from historical data from similar clinical trials using meta-analytic predictive prior (MAP) approach, the effective sample size is approximately 63 [[Schmidli, 2014](#)].

In the event that the placebo prior is different from what is presented here, this will be documented in the CSR.

Table 2 Statistical Analysis of Primary Endpoint

Endpoint(s)	

 PASI75 response at Week 12 (Day 85) 	
Analysis Method	
Bayesian Logistic Regression (using informative prior)	
Model Specification	
Outcome	$y_i = \text{Response (0/1) for participant } i$
Predictors	
 Treatment (categorical) Prior Biologic Use (categorical) Baseline PASI score (continuous) 
Unless stated otherwise the predictors (not including study treatment) will be centered around their estimated mean prior to inclusion in the model

Model	$y_i \sim \text{Ber}(p_i)$ $\text{logit}(p_i) = (\text{Treatment=Placebo}) \times \beta_1 + (\text{Treatment=GSK}) \times \beta_2 + (\text{Prior Biologic Use}^*) \times \beta_4 + (\text{Baseline PASI score}^*) \times \beta_5$
Prior distributions for coefficients (β)	β = fixed effect parameters associated to predictors 
 β_1: informative prior such that $\text{logit}^{-1}(\beta_1) \sim$ mixture of Betas* β_2: non-informative prior such that $\text{logit}^{-1}(\beta_2) \sim \text{Beta}(1/3, 1/3)$ Other β_k: non-informative priors of $N(0, SD=100)$ 
*Expected prior is a mixture of $Be(5.39, 69)$ and $Be(1/3, 1/3)$, weighted to 90% and 10% respectively. Final prior will be reported in the CSR.

Model Checking & Diagnostics	
See Section 5.1.1	

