Results Presentation	

 Posterior medians and 95% CrI of true response rate for each treatment group. Posterior medians and 95% CrI for the true difference in proportion of responders (GSK2982772 – placebo) and odds ratios of GSK2982772 to placebo. Probabilities that the true treatment difference is greater than a range of values of interest (e.g. 0%, 20%, 45%, 55%). See OPS outputs list for details. Probabilities that the true response rate on active is greater than a range of values of interest (e.g. 0%, 30%, 55%). See OPS outputs list for details. 	
Interim Analysis	

The interim analysis will estimate the predictive probability of meeting various decision criteria including:
 
 >55% probability that true difference in PASI75 response (GSK2982772 – Placebo) above 45% >97.5% probability that true difference in PASI75 response (GSK2982772 – Placebo) above 0% 	

Predictive probabilities will be calculated via simulation assuming a total sample size of 21 (14:7 for GSK2982772:Placebo).

The parameter posterior distributions from the Bayesian logistic regression analysis of interim data will be used to simulate predicted PASI75 responses for remaining trial subjects. For participants yet to be enrolled, average covariate values will be assumed.

The predicted data will be combined with the observed interim data and the Bayesian logistic model applied to assess the decision criteria. This process will be repeated for each run of the MCMC procedure. The proportion of times the decision criteria is met will be the predicted probability.

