5.2.4. Supplementary analyses

A supplementary analysis where the primary analysis is repeated using the Modified ITT population may be produced to assess the treatment effect in subjects able to complete at least 4 weeks of treatment. A frequency table of PASI response using this population would also be produced.

Off-treatment PASI data, collected following treatment discontinuation prior to Week 12, may be used for additional supplementary analyses if available.

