5.8. Interim Analyses

An interim analysis (IA) is planned to occur when at least six participants on GSK2982772 have completed the Week 12 (Day 85) visit or withdrawn from study treatment. The purpose of the IA is for internal decision making about future GSK2982772 trials and assess futility. The study may be stopped for futility if the probability of a positive outcome at the end of the trial is low based on the data available at the IA. The trial cannot be stopped early based on positive efficacy data.

Predictive probabilities will be calculated via simulation. The parameter posterior distributions from the Bayesian logistic regression analysis of interim data will be used to repeatedly simulate PASI75 response for remaining trial subjects. The predicted data will be combined with interim data to assess end of study criteria and calculate the proportion of times the decision criteria are met.

The data will be reviewed by an internal Data Review Committee. The committee will include the study statistician, the study pharmacokineticist and a limited number of GSK staff. A DRC charter will identify the specific staff to form part of the DRC, as well as detail the data to be reviewed, planned analyses, guidelines for the decision rules to be followed and a dissemination plan for interim decisions.

A subset of the outputs for the end of study will be produced for the IA. These will focus on efficacy data including, but not limited to:

- Summaries of PASI response data and change from baseline in PASI score by treatment and visit as outlined in Section [5.3.2](#) (Modified ITT population).
- Bayesian analysis of PASI75 response at Week 12 (Day 85) as outlined in Section [5.2.2](#) (Modified ITT population).
- Summaries of PK data and predicted target engagement as outlined in Section [5.5](#) (PK population).
- Summary of longitudinal model used to predict PASI score and the derived PASI75 at Week 16, outlined in Section [5.5.1](#), (conducted by CPMS on the ITT population).
- Summaries of disposition and psoriatic baseline characteristics (Randomised population).

Safety monitoring of blinded data will be conducted by the internal GSK Safety Review Team (SRT) at regular intervals throughout the study, see Section 8.2 of Protocol.

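### SAP 5.8 lists the interim PASI75 model on Week 4 completers, while the criteria it predicts belong to the ITT primary analysis, and nothing says how earlier losses are added back

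*SAP*

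**What the plan says.** **The interim model.** SAP 5.8 says that the "parameter posterior distributions from the Bayesian logistic regression analysis of interim data will be used to repeatedly simulate PASI75 response for remaining trial subjects". Those predictions are then joined to the interim data and tested against the end-of-study criteria. The paragraph names no analysis population. The output list in the same section names one: "Bayesian analysis of PASI75 response at Week 12 (Day 85) as outlined in Section [5.2.2](#) (Modified ITT population"). SAP 4 defines that set as "All participants in the ITT population who completed at least the Week 4 assessment".

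**The target.** The criteria are in the interim block of SAP Table 2, within SAP 5.2.2:
- more than 55% posterior probability that the PASI75 difference exceeds 45% (the 45% criterion);
- more than 97.5% posterior probability that it exceeds zero (the 0% criterion).

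For the analysis they belong to, the SAP says: "The primary analysis will be produced for the ITT population". Missing values there are non-responses. Protocol 9.4.1 has the same rule and applies it to early discontinuation as well.

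**The trigger.** The interim takes place "when at least six participants on GSK2982772 have completed the Week 12 (Day 85) visit or withdrawn from study treatment".

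**The final sample size.** Table 2 says: "Predictive probabilities will be calculated via simulation assuming a total sample size of 21 (14:7 for GSK2982772:Placebo"). SAP 3 says: "Replacement participants may be randomised (up to approximately 6) into the study at the discretion of the Sponsor", with the aim that about 21 complete Week 4.

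**The role of Modified ITT elsewhere.** The SAP version history calls it supplementary. At the final analysis it is optional: "A supplementary analysis where the primary analysis is repeated using the Modified ITT population may be produced".

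**The concern.** A predictive probability should forecast the analysis that will decide the result. Here the listed interim model excludes people whom the final analysis will include and whose outcome is already settled. An active participant who leaves before the Week 4 assessment helps to trigger the interim, is then left out of the prediction, and comes back at the end as a non-responder. No passage adds such participants to the completed data set.

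When the losses are on active, the forecast is generally too favourable compared with one that carries them. The predictive probability is the SAP's stated futility measure, and the interim also informs decisions on later trials of the compound. SAP version 2 itself expects more drop-outs because of COVID-19, so early losses are foreseen.

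The mismatch reaches only those lost before the Week 4 assessment. Protocol 7.1 keeps participants who stop treatment in the study unless they withdraw consent. Anyone who stops but completes the Week 4 assessment stays in Modified ITT.

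**Working it through.** **Inputs from the SAP.** Active prior Beta(1/3, 1/3). Placebo prior 0.9 × Beta(5.39, 69) + 0.1 × Beta(1/3, 1/3). Final size 14 active and 7 placebo. The two criteria of Table 2.

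**Assumptions, not in the documents.** Six known active outcomes at the interim, of which k are losses before Week 4 and r are responders. Placebo 0/3. No covariates.

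**1. Check against the plan's own figure.** SAP 3 gives about 99% probability of meeting the 0% criterion with 62% active response (7% + 55%) and 7% placebo response. Enumerating all 15 × 8 outcomes gives 99.7% with the Beta(3.5, 46.5) prior of SAP 3 and 98.1% with the mixture prior of SAP 5.2.2. The stated figure is reproduced to within about one point.

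**2. What the final analysis needs.** At 14:7, with 0, 1 or 2 placebo responders of 7, the 45% criterion is met from 8 active responders upward.

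**3. Formula.** With r responders among m = 6 − k Week 4 completers, a future active count Y out of R is beta-binomial(R; 1/3 + r, 1/3 + m − r). Future placebo counts follow the updated mixture. The predictive probability is the total weight of the (active, placebo) totals that meet the criterion.
- As listed: the k losses are absent, so R = 14 − m.
- Losses carried: the same response-rate posterior, with k fixed non-responders, so R = 14 − m − k.
- Losses carried and replaced: R = 14 − m again, with final active size 14 + k.

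**4. One worked case (k = 1, r = 3, m = 5).** Five more responders are needed.
- As listed, R = 9: Pr(Y ≥ 5) under beta-binomial(9; 3.33, 2.33) = 0.643.
- Carried, R = 8: Pr(Y ≥ 5) under beta-binomial(8; 3.33, 2.33) = 0.557.

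Allowing for the small chance of three or more placebo responders gives 0.642 and 0.556.

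**5. Results, 45% criterion.**

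| Losses k | Responders r | As listed | Carried, 14:7 | Carried and replaced |
|---|---|---|---|---|
| 1 | 1 | 0.026 | 0.012 | 0.022 |
| 1 | 2 | 0.222 | 0.153 | 0.197 |
| 1 | 3 | 0.642 | 0.556 | 0.605 |
| 1 | 4 | 0.937 | 0.910 | 0.922 |
| 1 | 5 | 0.998 | 0.997 | 0.997 |
| 2 | 2 | 0.432 | 0.267 | 0.300 |

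For one loss the largest shift is 0.642 − 0.556 = 0.086 at 14:7, and 0.642 − 0.605 = 0.037 with replacement.

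**6. Results, 0% criterion, one loss, as listed to carried at 14:7.** One responder 0.350 to 0.305; two 0.806 to 0.772; three 0.978 to 0.972. The largest shift is about 0.05.

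**7. No early loss.** With k = 0 and no early placebo loss, the two populations coincide and so do the results.

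**The case against.** **The link to Modified ITT is inferred.** The prediction paragraph names no population, SAP 5.1 makes ITT the default for efficacy, the output list is expressly not exhaustive, and detail is left to a charter that is not available. This stands as a limit on confidence. It does not remove the point, because the default yields where something else is specified, and the only interim PASI75 model listed is specified as Modified ITT. The choice looks deliberate, since the same list puts the longitudinal model on ITT.

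**Replacement is foreseen.** A simulated 21 built on Week 4 completers resembles the recruitment aim of about 21 reaching Week 4. This stands, and it more than halves the largest one-loss effect. Replacement is at the sponsor's discretion, however, and the replaced participant still belongs to the final ITT set.

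**The average gain depends on the loss rate.** I simulated the trigger at 62% completer response with assumed equal loss rates in both arms, spread evenly over Weeks 0 to 4. There was no replacement, and accrual was one participant every 0.67 or 2 weeks. Mean predictive probability of the 45% criterion:

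| Assumed loss | As listed | Carried | Actual final success |
|---|---|---|---|
| 5% | 0.62–0.63 | 0.59–0.61 | about 0.66 |
| 10% | 0.60–0.61 | 0.54–0.57 | 0.55–0.58 |
| 20% | about 0.6 | about 0.5 | about 0.38 |

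So the listed approach is not too high on average at 5%, slightly high at 10% and clearly high at 20%. This stands, and it is a reason to rate the point modestly.

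**Consequences are limited.** Futility stopping is permissive, there is no early stop for efficacy, and the committee also sees disposition. This stands too.

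**Conclusion.** The mismatch is in the text: the listed interim model is on Week 4 completers, and the criteria it predicts are on ITT with missing values as non-responders. Carrying one known early active loss lowers the 45% criterion's predictive probability by 0 to 0.09 at 14:7 and by at most about 0.04 with replacement. Two losses with two responders lower it from 0.43 to 0.27, or to 0.30 with replacements. For one loss the 0% criterion moves by at most about 0.05. These figures rest on the assumed interim counts and a model without covariates. I rate this a cheap improvement, with moderate confidence.

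Three stronger readings are tempting but not supported:
- **One loss costs 0.23.** Re-estimating the active rate with the loss in the denominator (3/6 instead of 3/5) takes 0.64 to 0.41. That also assumes that future participants are lost at the rate seen so far. At this trigger the rate is inflated, because a loss is known within four weeks and a response only at Week 12. The gap is not the effect of omitting one known outcome.
- **The trial would wrongly continue.** The documents give neither a futility cut-off nor a loss rate, so no change in the decision can be shown. Placebo losses can also push the other way.
- **The SAP breaches the protocol, or the final result is biased.** Protocol 9.4.1 lets the SAP depart from ITT, and the final ITT analysis is unchanged.

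**What to change.** In SAP 5.8 and the interim block of Table 2:
1. State that the predictive probability targets the ITT primary analysis, with missing values as non-responders.
2. Carry every ITT participant in either arm already lost before the Week 4 assessment into the completed data set as a non-responder. This uses only known outcomes and needs no assumed loss rate.
3. Let the simulated final size include replacements already randomised, instead of a fixed 14:7.
4. Keep the Modified ITT analysis as a supportive display.

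The cost is a few lines of SAP text and a small program change before the interim. The predictive probability will be somewhat lower when early losses occur, including COVID-19 losses unrelated to treatment. There is also a small price on the 0% criterion at the planned effect. In the simulation above, its average was already below actual final success, and carrying losses lowers it slightly further, for example from about 0.85 to about 0.83–0.84 at an assumed 10% loss with the faster accrual.

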6. SUPPORTING DOCUMENTATION

6.1. Appendix 1 Abbreviations and Trademarks

6.1.1. List of Abbreviations

Abbreviation	Description
AE	Adverse Event
A&R	Analysis and Reporting
BSA	Psoriasis body Surface Area
CI	Confidence Interval
Crl	Credible Interval
CSR	Clinical Study Report
C-SSRS	Columbia Suicide Severity Rating Scale
DRC	Data review committee
eCRF	Electronic Case Record Form
GSK	GlaxoSmithKline
IA	Interim Analysis
ITT	Intent-To-Treat
LS Mean	Least Squares Mean (or marginal mean)
MAR	Missing At Random
MMRM	Mixed Model Repeated Measures
MR	Modified Release
OPS	Output and Programming Specification
PASI	Psoriasis Area Severity Index
PCI	Potential Clinical Importance
PD	Pharmacodynamic
PK	Pharmacokinetic
PT	Preferred Term
QD	Once Daily
QTcB	Bazett's QT Interval Corrected for Heart Rate
QTcF	Frederica's QT Interval Corrected for Heart Rate
RNA-seq	Ribonucleic Acid Sequencing
SAE	Serious Adverse Event
SAP	Statistical Analysis Plan
SD	Standard Deviation
SE	Standard Error
sIGA	Static Investigator's Global Assessment of Disease Activity
SOC	System Organ Class
TEAR1	Target Engagement Assay RIP1
TMF	Trial Master File
ULN	Upper Limit of Normal

6.1.2. Trademarks

Trademarks of the GlaxoSmithKline Group of Companies	Trademarks not owned by the GlaxoSmithKline Group of Companies
None	None

